11.1.2. Recording of Adverse Events

AEs should be collected and recorded for each subject from the date the ICF was signed until the end of their participation in the study, ie, the subject has discontinued or completed the study. All AEs experienced by a subject, irrespective of the suspected causality, will be monitored until the event has resolved or stabilized, until any abnormal laboratory values have returned to baseline or stabilized at a level acceptable to the Investigator and Sponsor medical representative, until there is a satisfactory explanation for the changes observed, or until the subject is lost to follow-up.

Any new SAEs that are suspected to be related to study drug occurring up to 28 days after the last administration of study drug should be reported to ICON according to Section 11.1.5. Adverse events may be volunteered spontaneously by the study subject, discovered by the study staff during physical examinations, or by asking an open, nonleading question such as "How have you been feeling since you were last asked?" All AEs and any required remedial action will be recorded. The nature of AE, date (and time, if known) of AE onset, date (and time, if known) of AE outcome to date, severity, and action taken with the study drug because of the AE will be documented together with the Investigator's assessment of the seriousness on the AE and causal relationship to study drug and/or study procedure.

All AEs should be recorded individually unless, in the opinion of the Investigator, the AEs constitute components of a recognized condition, disease, or syndrome. In the latter case, the condition, disease, or syndrome should be named rather than each individual symptom. The date (and time, if known) that the Investigator or study site is first made aware of the AE (or any subsequent follow-up information is received) will be documented. The AEs will be coded using the current version of the Medical Dictionary for Regulatory Activities (MedDRA).

Each AE will be assessed by the Investigator with regard to the categories discussed in the sections below.

11.1.2.1. Intensity

The Investigator will assess all AEs for severity utilizing the NCI-CTCAE grading scale (Version 5.0). AEs not contained within CTCAE Version 5.0 will be rated on a five-point scale (Table 8):

Version 1.0 Page 80 of 145

Table 8: Severity Grading Scale

Mild (Grade 1)	Mild events are those which are easily tolerated with no disruption of normal daily activity.	
Moderate (Grade 2)	Moderate events are those which cause sufficient discomfort to interfere with daily activity.	
Severe (Grade 3)	Severe events are those which incapacitate and prevent usual activity.	
Life-threatening (Grade 4)	An adverse event that has life-threatening consequences, for which urgent intervention is indicated, that puts the subject at risk of death at the time of the event if immediate intervention is not undertaken, or that causes blindness or deafness.	
Fatal (Grade 5)	The termination of life as a result of an adverse event.	

CONFIDENTIAL

When changes in the intensity of an AE occur more frequently than once a day, the maximum intensity for the event should be noted for that day. Any change in severity of signs and symptoms over a number of days will be captured by recording a new AE, with the amended severity grade and the date (and time, if known) of the change.

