11.1. Adverse Events

11.1.1. Definitions

11.1.1.1. Adverse Event

An AE is any untoward medical occurrence in a study-subject administered IMP. The AE does not necessarily have a causal relationship with this treatment. An AE can therefore be any unfavorable and unintended sign (including a clinically significant abnormal laboratory finding), symptom, or disease temporally associated with the use of an IMP, whether or not considered related to the IMP. Adverse events may include the onset of new illness and the exacerbation of preexisting conditions.

Other untoward events occurring in the framework of a clinical study will be recorded as AEs, eg, those occurring during treatment-free periods (including Screening or post-treatment follow-up periods), in association with study-related procedures and assessments, or under placebo. For IMPs, lack of efficacy may be an expected potential outcome and should not be reported as an AE, unless the event is unusual in some way, eg, greater in severity.

Concomitant illnesses, which existed prior to entry into the clinical study, will not be considered AEs unless they worsen during the treatment period. Preexisting conditions will be recorded as part of the subject's medical history.

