14.6. Safety Assessment

Safety variables will include AEs, PE findings, vital signs, ECGs, and laboratory values.

The extent of exposure to XmAb18087 monotherapy, as well as exposure in combination with pembrolizumab, will be summarized by dose cohort based on the number of infusions administered and the number of treatment cycles completed, as well as the total dose received. Additional summaries of drug exposure will be provided based on the PK parameters described in Section 13. Reasons for missed infusions or early permanent discontinuation of XmAb18087 will be reported.

Summary tables and listings will be provided for all reported AESC.

Adverse events will be coded using the latest version of MedDRA. The verbatim term recorded by the Investigator will be mapped to System Organ Class (SOC) and Preferred Term using MedDRA.

Treatment-emergent AEs are defined as events with onset dates on or after the start of study treatment or events that are present before the first infusion of XmAb18087 and subsequently worsen in severity.

Adverse-event-related endpoints include the following:

- TEAEs
- Treatment-emergent SAEs (TESAEs)
- Treatment-related TEAEs (for XmAb18087 or for pembrolizumab, if they can be distinguished)
- Treatment-related TESAEs (for XmAb18087 or for pembrolizumab, if they can be distinguished)
- TEAEs by severity that are defined by NCI-CTCAE, Version 5.0
- TEAEs resulting in the permanent discontinuation of XmAb18087 and/or pembrolizumab.

All AE-related endpoints will be summarized by MedDRA SOC and preferred term. At each level of summation, subject will be counted once under the greatest severity and strongest study drug relationship. All AEs will be included in the listings.

The hematology, chemistry, and other laboratory values and change from baseline values will be summarized descriptively for each scheduled assessment time point and grouped by dosing cohort. The baseline value for each laboratory value is defined as the last assessment performed on or prior

Version 1.0 Page 102 of 145

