## **11. SAFETY ANALYSES**

### **11.1. Adverse Events**

AEs and serious AEs will be graded according to the National Cancer Institute's Common Terminology Criteria for Adverse Events (NCI-CTCAE v5.0) (except CRS, which is graded using the American Society for Transplantation and Cellular Therapy (ASTCT) CRS Consensus Grading) and be described using the MedDRA by system organ class, preferred term, severity, and relationship to XmAb18087.

Treatment-emergent AEs (TEAEs) will be marked. TEAEs are defined as events with onset dates on or after the start of study treatment or events that are present before the first infusion of XmAb18087 and subsequently worsen in severity.

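### Recording each multi-day grade change as a new, newly dated AE lets an AE that began before dosing and improved on treatment be marked treatment-emergent in the SAP listings

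*Protocol*

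**What the plan says.** **Collection.** Protocol 11.1.2 starts AE recording at consent: "AEs should be collected and recorded for each subject from the date the ICF was signed". Screening runs from Day -28 to Day -2 (Protocol 7.9.1.1), so AE records that predate dosing can exist.

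**Grade changes.** Protocol 11.1.2.1: "Any change in severity of signs and symptoms over a number of days will be captured by recording a new AE", and the new record comes "with the amended severity grade and the date (and time, if known) of the change". The one exception is for changes more often than once a day, where "the maximum intensity for the event should be noted for that day".

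**Earlier illness.** Under Protocol 11.1.1.1, illnesses that existed before study entry "will not be considered AEs unless they worsen during the treatment period".

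**TEAE definition.** Protocol 14.6: "Treatment-emergent AEs are defined as events with onset dates on or after the start of study treatment". SAP 11.1 repeats this: "TEAEs are defined as events with onset dates on or after the start of study treatment". Both add a second limb, joined by *or*, for an event that is already there before the first XmAb18087 infusion and gets worse afterwards.

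**How the flag is set.** SAP 5.2.2.1 and Appendix 1 work from the AE start date, imputing it where it is missing, to decide whether an AE is treatment-emergent.

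**Output.** Protocol 14.6 counts each subject once per MedDRA level, at the greatest severity. SAP sections 2 and 5.1 replace tables with listings, because only 4 subjects were enrolled (2 in Part A, 2 in Part C). SAP 11.1 keeps the TEAE mark in those listings.

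**The concern.** The recording rule works at the level of a grade, while the TEAE definition is phrased at the level of an event. Neither document says how to get from one to the other. There is no rule that links successive records of one episode, carries the episode's start date forward, or treats a record created by improvement differently from one created by worsening.

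What is at stake is the meaning of the TEAE mark. TEAE incidence is listed first among the primary safety endpoints (Protocol 14.3.1; also SAP 3.3), and with listings only, the mark is what remains of that endpoint. An AE that arose before any drug was given and eased on treatment should not appear as an event that emerged on treatment. The error has one direction: it can only add TEAE marks.

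**Working it through.** There is no planned figure to reproduce. The check applies the recording rule and the TEAE definition to two assumed AE histories. The documents do not show that either history occurred.

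**Rules applied**
1. Each change of grade on a different day opens a new AE record dated at the change (Protocol 11.1.2.1).
2. A record is a TEAE if its start date is on or after first dose (first limb), *or* if the event predates first infusion and later worsens (second limb) (Protocol 14.6, SAP 11.1).
3. The flag is read from the AE start date (SAP 5.2.2.1, Appendix 1).

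**History (a): starts before dosing, improves on treatment.** Grade 2 from Day -5, Grade 1 from Day 3, resolved Day 6.

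| Record | Start | Grade | First limb | Second limb | Marked TEAE |
|---|---|---|---|---|---|
| 1 | Day -5 | 2 | no | no (no worsening) | no |
| 2 | Day 3 | 1 | yes | not needed | **yes** |

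As written there is 1 TEAE row. Read as one episode, it starts on Day -5 and its highest post-dose grade (2, on Days 1 to 2) does not exceed its highest pre-dose grade (2), so there are 0 TEAEs.

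**History (b): starts on treatment.** Grades 1, 2, 3, 2, 1 on separate days. With k grade changes there are k + 1 records; here k = 4, so 4 + 1 = 5 records, all marked. Read as one episode, there is 1 TEAE with maximum Grade 3.

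**Subject-level count, if one were made under Protocol 14.6.** History (b) counts one subject either way. History (a) counts one subject as written and none as an episode.

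**What the second limb shows.** If each post-dose worsening already opens a post-dose record, the first limb catches it and the second limb has almost nothing left to do. The second limb has a purpose only if an event is a continuing episode whose start stays where it was. The definition therefore appears to have been written for episodes, while the recording rule supplies grade-level pieces.

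**Scope of history (a).** Illness that predates study entry is not an AE unless it worsens. The case therefore needs an AE that arises between consent and first dose, is still present at dosing, and then drops a grade without resolving.

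**The case against.** The strongest reply is that *event* already means the episode. The second limb treats something present before infusion as the same continuing event. Protocol 11.1.2.1 speaks of the date of the change and does not call it an onset, and Protocol 11.1.2 lists AE onset separately. That is probably what the authors intended. It does not settle the matter, because the same sentence calls the entry a new AE, the SAP flag rests on the start date, and no instruction tells a programmer how to rebuild episodes. The eCRFs, which the SAP says should be read alongside it, are not available here and may already link such records.

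A second reply is that a reader can see through any wrong mark. Dates are listed as recorded, grade and preferred term are shown, and adjoining rows in 4 subjects are easy to recognise. This stands, and it limits the harm.

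Three stronger inferences are tempting, and the documents do not support them:

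- *AESC durations are broken by the split*, for example 4 days at Grade 3 and then 4 days at Grade 4 thrombocytopenia missing the 7-day criterion. Protocol 7.8 defines that criterion as time at Grade 3 or above, which 4 + 4 = 8 days meets, and it admits laboratory values directly. During the run-in the SRC reviews all available safety data (Protocol 7.7). Nothing derives AESC duration from single AE records.
- *TEAE incidence shifts sharply*, since one subject of two in a Part is 50%. The SAP plans no incidence table, so no planned result moves by that amount.
- *One episode is counted as several TEAEs.* This is true of listing rows only. The once-per-subject rule in Protocol 14.6 prevents it in any subject-level count.

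**Conclusion.** The wording gap is real and its consequence is minor. Taken literally, the recording rule and the first limb of the TEAE definition mark an improving AE that began before dosing as treatment-emergent, against the evident purpose of the second limb. They also spread one on-treatment episode over several TEAE rows. The effect is confined to TEAE marks and row counts in the listings for 4 subjects. It does not reach AESC assessment or any planned incidence figure.

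The conclusion assumes that the date of a grade change is entered as the new record's start date, and that the eCRF does not already tie such records together. Whether any of the 4 subjects had such an AE cannot be told from the documents.

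**What to change.** Add a short rule to SAP 11.1:

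- Treat consecutive records of the same preferred term with no gap between them as one episode.
- Mark the episode as a TEAE only if it starts on or after first dose, or if its highest grade after first dose exceeds its highest grade before first dose.
- List episode onset, resolution and maximum grade, with the grade history beneath.

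The rule uses data already collected. Its cost is a few lines of text, simple programming, and a brief manual check that the joined records are one episode. It also involves one choice that the SAP should state openly. An episode at Grade 3 before dosing that had eased to Grade 1 by first dose and then rose to Grade 2 would not be marked, because the comparison is with the highest pre-dose grade. Changing the protocol's recording rule, for instance by adding a linking identifier, would bring little now that the study has been terminated.

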11.1.2.2. Causality

The Investigator will assess the causality/relationship between the IMP and the AE. One of the following categories should be selected based on good medical and scientific judgment, considering the definitions in Table 9 and all contributing factors.

Version 1.0 Page 81 of 145

Table 9: Causality Grading Scale

Related	A clinical event, including laboratory test abnormality that occurs in a plausible time relationship to treatment administration, and which concurrent disease or other drugs or chemicals cannot explain. The response to withdrawal of the treatment (dechallenge ^a) should be clinically plausible. The event must be definitive pharmacologically or phenomenologically, using a satisfactory rechallenge ^b procedure if necessary.
Probably Related	A clinical event, including laboratory test abnormality, with a reasonable time sequence to administration of the treatment, unlikely to be attributed to concurrent disease or other drugs or chemicals, and which follows a clinically reasonable response on withdrawal (dechallenge). Rechallenge information is not required to fulfill this definition.
Possibly Related	A clinical event, including laboratory test abnormality, with a reasonable time sequence to administration of the treatment, but which could also be explained by concurrent disease or other drugs or chemicals. Information on treatment withdrawal may be lacking or unclear.
Unlikely Related	A clinical event, including laboratory test abnormality, with a temporal relationship to treatment administration that makes a causal relationship improbable, and in which other drugs, chemicals, or underlying disease provide plausible explanations.
Not Related	A clinical event, including laboratory test abnormality, with little or no temporal relationship with treatment administration. May have negative dechallenge and rechallenge information. Typically explained by extraneous factors (eg, concomitant disease, environmental factors, or other drugs or chemicals).

AE = adverse event.

11.1.2.3. Action Taken with Study Treatment

Action taken with XmAb18087 (and pembrolizumab, when applicable) will be reported as one of the following:

- Dose not changed
- Dose reduced
- Drug interrupted
- Drug withdrawn
- Not applicable

11.1.2.4. Outcome

Outcome will be defined as follows:

- Death related to adverse event
- Not recovered or not resolved

Version 1.0 Page 82 of 145

^a Dechallenge is when a drug suspected of causing an AE is discontinued. If the symptoms of the AE disappear partially or completely, within a reasonable time from drug discontinuation, this is termed a positive dechallenge. If the symptoms continue despite withdrawal of the drug, this is termed a negative dechallenge. Note that there are exceptions when an AE does not disappear upon discontinuation of the drug, yet drug-relatedness clearly exists (for example, as in bone marrow suppression, fixed drug eruptions, or tardive dyskinesia).

b Rechallenge is when a drug suspected of causing an AE in a specific subject in the past is readministered to that subject. If the AE recurs upon exposure, this is termed a positive rechallenge. If the AE does not recur, this is termed a negative rechallenge.

- Recovered or resolved
- Recovered or resolved with sequelae
- Recovering or resolving
- Unknown

11.1.3. Preidentified Immune-Mediated Adverse Events

See the pembrolizumab package insert (Keytruda[®] Package Insert, 2020) for a description of potential IRAEs. Guidelines for the management of IRAEs can be found in Table 18 and Appendix E.

11.1.4. Adverse Events of Special Interest

IRAEs (Part B only) and infusion reactions (hypersensitivity reactions and CRS) are designated events of special interest in this protocol. Refer to Section 11.3.

11.1.4.1. Deaths

Should a death occur within the study period or within 28 days after the last administration of study drug (or until the subject initiates other anticancer therapy, whichever comes first), an AE form and an SAE form should be completed, detailing the AE that resulted in the death (death is an outcome, not an event). The SAE must be reported to the Medical Monitor within 24 hours. The report should contain a comment regarding the coinvolvement of progression of disease, if appropriate, and should assign main and contributory causes of death.

11.1.4.2. Pregnancy

The teratogenic potential of XmAb18087 is unknown. Based on its mechanism of action, pembrolizumab can cause fetal harm when administered to a pregnant woman; however, there are no available human data informing the risk of embryo-fetal toxicity (Keytruda® Package Insert, 2020). The Investigator and Sponsor have a responsibility to monitor the outcome of all pregnancies, including pregnancies in female partners of male participants, reported during the clinical study.

Pregnancy alone is not regarded as an AE unless there is a suspicion that the IMP may have interfered with the effectiveness of a contraceptive medication. Elective abortions without complications should not be regarded as AEs, unless they were therapeutic abortions (see below). Hospitalization for normal delivery of a healthy newborn should not be considered an SAE. All notifications of pregnancy should be documented and reported through 120 days following cessation of study treatment (or through 30 days following cessation of study treatment if the subject initiates new anticancer therapy), whether or not there is an associated AE or SAE.

Each pregnancy notification must be reported by the Investigator to the Sponsor and ICON within 24 hours after becoming aware of the pregnancy. The Investigator must follow-up and document the course and the outcome of all pregnancies even if the subject was withdrawn from the clinical study or if the clinical study has finished. The follow-up period will be deemed to have ended when the health status of the child has been determined on its birth.

Version 1.0 Page 83 of 145

All outcomes of pregnancy must be reported by the Investigator to the Sponsor and ICON on the pregnancy outcome report form within 24 hours after he/she has gained knowledge of the normal delivery or elective abortion, or other outcome.

Any SAE that occurs during pregnancy must be recorded on the SAE report form (eg, maternal serious complications, therapeutic abortion, ectopic pregnancy, stillbirth, neonatal death, congenital anomaly, birth defect) and reported within 24 hours of awareness in accordance with the procedure for reporting SAEs.

11.1.5. Reporting Serious Adverse Events

The Investigator will review each potential SAE and evaluate the intensity and the causal relationship of the event to IMP. All potential SAEs will be recorded from signing of informed consent until the end of the subject's participation in the study: ie, the subject has discontinued or completed the study, except for the long-term follow-up period. During the long-term follow-up period, only SAEs that come to the attention of the Investigator and that the Investigator believes to have a reasonable causal relationship to the IMP will be reported.

The Investigator is responsible for reporting SAEs related to pembrolizumab to regulatory authorities per reporting guidelines.

The Investigator is responsible for providing notification to ICON of any potential SAE, whether deemed IMP-related or not, that a subject experiences during his/her participation in study within 24 hours of becoming aware of the event. ICON will provide the information to the Sponsor.

The initial SAE form should be completed and emailed to with the following information:

- Study number
- Subject number
- Gender
- Year of birth
- Name of PI and full clinical site address
- Name of the reporter
- SAE event term
- Details of SAE
- Criterion for classification as "serious"
- Study drug name, dose, and treatment start date
- Date of SAE onset
- Date of SAE first awareness (by Investigator or study site staff)
- Causality assessment

[figure not shown]
Version 1.0 Page 84 of 145

18 August 2020

ICON will request clarification of omitted or discrepant information from the initial notification. The Investigator or an authorized delegate is responsible for providing the requested information to ICON within 24 hours of the request.

Initial reports of SAEs must be followed up as soon as possible with detailed descriptions; this may include clear photocopies of other documents as necessary (eg, hospital reports, consultant reports, autopsy reports, etc.) with the study subject's personal identifiers removed. All relevant information obtained by the Investigator through review of these documents will be recorded and forwarded to ICON within 24 hours of receipt of the information.

If a new SAE report form for the same SAE is completed, then the Investigator must sign and date the SAE form and mark the form as "follow-up." ICON and/or the Sponsor may also request additional information on the SAE in order to obtain the full clinical picture, to which the PI or an authorized delegate must respond to ICON within 24 hours of the request.

- 1. E-mail your SAE form to the study specific e-mail address above.
- 2. Provide ICON with the name of the PI, your name, the telephone number where you can be reached and the protocol number and title.
- 3. Immediately forward the SAE form and any supporting documentation to ICON; this must be done within 24 hours of becoming aware of the event.

